#### **Start of Open-label Period Date**

For subjects entering in the ALN open-label period, the end of double-blind period date is the beginning of the open-label period date. All scheduled

assessments occurring on this date are attributed to the double-blind period. The open-label ALN dose on the day is considered as occurring in the open-label follow-up period. Any adverse event or concomitant medication with a start date on this date is considered having started in the open-label follow-up period.

### **End of 24-Month ALN Study Period Date**

End of the 24-Month period date is defined as the following:

1. Month 24 visit date if this date is prior to or on Study Day 731 + 30 days
2. End of study date or Study Day 761, whichever occurs first, for subjects who did not complete the Month 24 visit prior to Study Day 761 days

The Month 24 visit date is defined as the latest assessment collected at Month 24.

### **Last Dose Date**

The last dose date in double-blind or open-label period, whichever is later

### **Wrong Dose Date in Double-blind Period**

For subjects who are randomized to ALN and accidentally receive romosozumab, the wrong dose date is when they receive the 1st SC administration of romosozumab in the double-blinded period. For subjects who are randomized to romosozumab and receive oral ALN in the double-blinded period, if the wrong oral IP box is dispensed on Day 1, the wrong dose date is the 1st oral dose date; otherwise, the wrong dose date is when the 1st wrong oral IP box is dispensed because the oral ALN dosing dates are not collected in eCRF.

## **6.1.3 Study Time Intervals**

### **On-Study Period**

The time period from the enrollment date to the end of study date, inclusive

### **Double-blind Period**

The time period from the enrollment date to the end of double-blind period date, inclusive

### **Open-label ALN Period**

The time period from the end of double-blind period date to the end of study date, inclusive

### Month 12 to Month 24 ALN Study Period

For subjects entering in the ALN open-label period, the time period from the end of double-blind period date to the Month 24 visit date, study day 761, or end of study date, whichever is the earliest, inclusive.

The Month 24 visit date is defined as the latest assessment collected at Month 24.

### 24-month ALN Study Period

The time period from the enrollment date to the Month 24 visit date, study day 761, or end of study date, whichever is the earliest, inclusive

### Primary Analysis Period

The time period from the enrollment date to the end of primary analysis period date, inclusive

### Overall Study Period

If the study will continue to the final analysis, the overall study period is defined as the time period from the enrollment date to the end of final analysis period date, inclusive.

#### 6.1.4 Fracture Risk Assessment Tool: 10-year Probability of Major Osteoporotic Fracture (FRAX)

FRAX is a computer-based algorithm (<http://www.shef.ac.uk/FRAX>) that provides country/ethnicity-specific models for the assessment of fracture probability in men and women [Kanis et al, 2001,2008]. The approach uses clinical risk factors to estimate 10-year probability of a major osteoporotic fracture (hip, clinical spine, forearm or humerus) or of a hip fracture alone. The estimate of probability can be calculated with clinical risk factors alone, or additionally with baseline femoral neck BMD. The clinical risk factors used for the calculation include sex, age, body mass index (BMI), a prior fragility fracture, parental history of hip fracture, current tobacco smoking, ever long-term use of oral glucocorticoids, rheumatoid arthritis, other causes of secondary osteoporosis, and daily alcohol consumption of 3 or more units daily.

#### 6.2 Subject Disposition

##### Enrolled (Randomized)

Individuals are considered enrolled if they have been assigned a randomization number. Enrolled individuals are referred to as “subjects”.

## Exposed to Investigational Product

Subjects are defined as exposed if they have a value for the sum of investigational product dose that exceeds zero.

## Enrolled Into Sub-study

Randomized subjects who sign the informed consent for the sub-study are considered enrolled into the sub-study.

### 6.3 Arithmetic Calculations

#### Age at Randomization Date

Number of whole years from a subject's birth date to the randomization date as recorded on the eCRF.

#### Estimated Glomerular Filtration Rate (eGFR) (mL/min) Using Modification of Diet in Renal Disease (MDRD) for Females

Conventional units (creatinine as mg/dL; age in years):

$$\text{eGFR (mL/min/1.73 m}^2\text{)} = 175 \times (\text{Serum creatinine})^{-1.154} \times [\text{Age}]^{-0.203} \times (0.742 \text{ if female}) \times (1.212 \text{ if African American})$$

SI units (creatinine as  $\mu\text{mol/L}$ ; age in years):

$$\text{eGFR (mL/min/1.73 m}^2\text{)} = 175 \times (\text{Serum creatinine}/88.4)^{-1.154} \times [\text{Age}]^{-0.203} \times (0.742 \text{ if female}) \times (1.212 \text{ if African American})$$

#### Percent Change From Baseline

The change from baseline divided by baseline value and multiplied by 100:

$$(\text{Change From Baseline} / \text{Baseline}) * 100$$

#### Subject Incidence Rate for Adverse Events

The subject incidence rate for a given event in a given time period (double-blind period, primary analysis period, or overall study period) is defined as the number of subjects with  $\geq 1$  reported occurrence of the event divided by the number of subjects who are at risk for having the event in the beginning of the given time period. For subjects with multiple occurrences of the same event in a given period, the event will only be counted once per subject.

#### Subject Years On-Study in Double-blind Period

Defined for a given subject as the number of days between the first dose date to end of double-blind period date, inclusive, divided by 365.25 (ie,  $[\text{End of Double-blind Period Date} - \text{First Dose Date} + 1] / 365.25$ ). The subject years on study will be summed over all subjects within a treatment group. For subjects who never received a dose of investigational product, the randomization date will be used.

### **Subject Years On-Study in Primary Analysis Period**

Defined for a given subject as the number of days between the first dose date to end of primary analysis period date, inclusive, divided by 365.25 (ie,  $[\text{End of Primary Analysis Period Date} - \text{First Dose Date} + 1] / 365.25$ ). The subject years on study will be summed over all subjects within a treatment group. For subjects who never received a dose of investigational product, the randomization date will be used.

### **Subject Years On-Study in Overall Study Period**

Defined for a given subject as the number of days between the first dose date to end-of-study date, inclusive, divided by 365.25 (ie,  $[\text{End of Study Date} - \text{First Dose Date} + 1] / 365.25$ ). The subject years on study will be summed over all subjects within a treatment group. For subjects who never received a dose of investigational product, the randomization date will be used.

### **Time to First Event in Double-blind Period**

Time to event is calculated as the elapsed time interval in days between the occurrence date of the event of interest or censorship and the reference date:

$$\text{Time Interval} = \text{Date of the Event or Censorship} - \text{Reference Date} + 1$$

Note for fracture endpoints, the date of event is the date that confirms the fracture provided by the central imaging reader (eg, date of x-ray used by the central imaging vendor to verify the fracture, or surgical report or discharge summary if x-ray date is not available). For adverse events, nonvertebral fractures, and other events, which can be assessed at any time, subjects who did not have any event will be censored on the date of last evaluation for the event, which is the End of Double-blind Study Period; for vertebral fractures, which have to be identified on scheduled assessments, subjects who did not have any event will be considered censored at the last post-baseline assessment or day 1 if there were no post-baseline assessment.

The reference date will be the randomization date for efficacy events or first dose date for safety endpoints.

### **Time to First Event in 24-month Study Period**

The time to event in the 24-month study period is defined similarly as for time to first event in double-blind period. Subjects who did not have any event will be censored on the date of last evaluation for the event, which is the end of 24-month ALN study period date.

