#### **10.5.1.3 Standard Analyses for Time-to-event Endpoints**

All time-to-event endpoints will be summarized descriptively using the Kaplan-Meier estimates at time point(s) of interest (SAS code in [Section 13.4.7](#)). Further analysis using a stratified Cox proportional hazards model controlling for age strata with presence or absence of severe vertebral fracture at baseline, baseline total hip BMD T-score, and treatment as the independent variable will also be provided (SAS code in [Section 13.4.8](#)). The significance of the treatment effect between treatment arm and control arm will be assessed based on the Cox proportional hazards model. The estimated hazard ratio, corresponding 95% confidence interval, and the p-value of the score test from the model will be provided. In addition, the point estimate of the adjusted risk difference (difference in Kaplan-Meier estimates at the time point of interest, control arm - treatment arm) and the corresponding 95% confidence interval will be provided

using the inverse variance-weighted method (SAS code in [Section 13.4.14](#)). For 12 months analysis, subjects without having the event of interest in the double-blind period will be censored at the end of double-blind period date. For 24 months analysis, subjects without having the event of interest in the study will be censored at the end of 24-month study period.

The proportional hazards assumption will be examined visually using log-log survival plots versus time and plots of Schoenfeld residuals versus time ([Schoenfeld, 1982](#)). If the proportional hazards assumption is violated, a piecewise Cox proportional hazards model assuming proportional hazards in the 1st year, the 2nd year, and all remaining years thereafter, will be used.

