##### Time-to-event analysis based on full analysis set

A supportive analysis for new vertebral fracture through Month 24 will be performed based on time-to-first new vertebral fracture using the stratified Cox proportional hazards model as described in [Section 10.5.1.3](#).

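### The SAP gives conflicting censoring rules for the supportive time-to-event analysis of new vertebral fracture through Month 24; read literally, the period-end rule counts time without a film as fracture-free

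*SAP*

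**What the plan says.** SAP Section 10.5.2.2 lists, as support for the co-primary new vertebral fracture result, an analysis of "time-to-first new vertebral fracture using the stratified Cox proportional hazards model". Its heading places it on the full analysis set, and it refers to Section 10.5.1.3 for the model.

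Three places bear on how a woman without an event is censored:

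- **Section 6.3, Time to First Event in Double-blind Period.** Events that can be assessed at any time are censored at the period end. Vertebral fractures have their own rule: "subjects who did not have any event will be considered censored at the last post-baseline assessment or day 1 if there were no post-baseline assessment".
- **Section 6.3, Time to First Event in 24-month Study Period.** The first sentence reads "The time to event in the 24-month study period is defined similarly as for time to first event in double-blind period". The second puts censoring for event-free subjects at their last evaluation, "which is the end of 24-month ALN study period date".
- **Section 10.5.1.3.** For 24-month analyses, "subjects without having the event of interest in the study will be censored at the end of 24-month study period". No vertebral exception is made.

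Section 6.1.2 defines the end of the 24-month period. It is the Month 24 visit date if that falls on or before Study Day 761. Otherwise it is the end-of-study date or Study Day 761, whichever is earlier. Neither of those last two dates requires a film.

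**The concern.** A radiographic fracture can be seen only on a film. A woman whose last film was at Month 12 is known to be fracture-free to Month 12 and no further. Censoring her at the period end keeps her in the risk set at Month 24, when a fracture in her could not have been found.

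The full analysis set adds a second group. It includes women with no post-baseline film at all, whom the primary vertebral set (Section 7.1) generally excludes. Under the period-end rule they would enter as fracture-free time.

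The per-protocol support for this endpoint carries the last vertebral status forward (Sections 10.5.2.2 and 9.2.2), and the covariate analyses use the primary imputation (Section 10.5.2.3). The time-to-event analysis is the only supportive analysis in Section 10.5.2.2 not built on that imputation. Under the literal rule it would still treat unseen as unfractured. With two rules on the page, the choice could also be made after unblinding.

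**Working it through.** **1. The rules side by side, for a woman with no event**

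| Situation | Last-film rule | Period-end rule |
|---|---|---|
| Month 24 film taken at the visit | that film | Month 24 visit date: the same or nearly so |
| Withdrew, early-termination film taken | that film | end-of-study date: nearly the same |
| On study, Month 12 film only | about Day 366 | up to Day 761, so up to 761 − 366 = 395 unfilmed days |
| On study, no post-baseline film | day 1 | up to Day 761 |

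The rules differ materially only in the last two rows, and for women who withdraw without a film.

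**2. The plan's own figure**

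Inputs from SAP Sections 3.2.1 to 3.2.3: 4.4% on alendronate at two years; a 50% reduction, so 2.2%; 2,000 per arm; 2-sided chi-square without continuity correction. With Hochberg over two endpoints, alpha is taken as 0.025.

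- Null SE = √(2 × 0.033 × 0.967 / 2,000) = 0.00565
- Alternative SE = √((0.044 × 0.956 + 0.022 × 0.978) / 2,000) = 0.00564
- Power = Φ((0.022 − 2.241 × 0.00565) / 0.00564) = Φ(1.66) ≈ 95.1%

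This reproduces the stated 95%. Simulation with Hochberg gave 95.1% to 95.7%. The censoring rule does not enter the calculation.

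**3. Expected size by hand**

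The documents give no rate of missing Month 24 films. Assume 5% of alendronate and 10% of romosozumab subjects still on study have none. Under the period-end rule they stay in the Month 24 risk set, so the second-year hazard is multiplied by 0.95 and 0.90.

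- Second-year hazard ratio multiplied by 0.90 / 0.95 = 0.947
- Month 12 detections on alendronate, with 10% first-year dropout: 0.90 × 2.2% = 1.98%
- Month 24 detections, with 8% second-year dropout: 0.90 × 0.92 × 2.2% × 0.95 = 1.73%
- Share of detections at Month 24: 1.73 / (1.98 + 1.73) = 0.47
- Shift in the 24-month log hazard ratio: 0.47 × ln(0.947) = −0.026, about 2.5%

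**4. Simulation of both rules**

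Exponential fracture times and dropout as in the plan; films at Months 12 and 24; unadjusted Cox hazard ratio with score test. The first two rows assume no early-termination films; the others assume one is obtained in half of withdrawals.

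| Missing Month 24 film, ALN / romosozumab | True effect | HR, last film | HR, period end | Rejection, last film / period end |
|---|---|---|---|---|
| 0% / 0% | 50% reduction | 0.501 | 0.501 | 95.1% / 95.1% |
| 5% / 5% | 50% reduction | 0.499 | 0.499 | 94.8% / 94.9% |
| 5% / 10% | 50% reduction | 0.496 | 0.484 | 94.9% / 96.0% |
| 10% / 5% | 50% reduction | 0.499 | 0.511 | 95.9% / 93.7% |
| 5% / 10% | none | 1.002 | 0.978 | 5.0% / 4.7% |
| 5% / 20% (extreme) | none | 1.005 | 0.932 | 5.0% / 7.5% |

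In the 5% / 10% case, 0.484 / 0.496 = 0.976, a 2.4% shift that agrees with step 3. With 5% missing in each arm the alendronate 24-month Kaplan-Meier estimate falls from 4.3% to 4.2%.

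Dropout alone moves nothing here, because women who leave before a scheduled film are out of its risk set under either rule. The share never filmed is about 10% of each arm if no early-termination film is taken, 5% if half are, and zero if all are.

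**The case against.** The strongest reply is that the right rule is already in the SAP and applies. The double-blind definition separates x-ray events from events assessable at any time, and the 24-month definition adopts it. Its second sentence can be read as restating only the any-time branch with a new period end. It still speaks of the last evaluation for the event, which for an x-ray event is the last film.

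Section 10.5.1.3 gives the same blanket rule for 12 months, where Section 6.3 states the exception outright, so its silence at 24 months may be shorthand. New vertebral fracture through Month 12 is analysed by logistic regression. The 24-month Cox analysis is thus the one planned time-to-event analysis of this endpoint, and the one most in need of the vertebral clause.

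This makes the last-film reading plausible and perhaps intended. It does not remove the conflict. The second sentence is not limited to events assessable at any time, and Section 10.5.2.2 sends the analyst to Section 10.5.1.3, which omits the exception. The code fragments in Section 13.4 are redacted, so the programmed rule cannot be checked; that is not held against the plan.

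The reply is also right that exposure is narrow. The Month 24 film is scheduled at the visit that ends the period, and Protocol Sections 7.3.13 and 7.3.16 ask for a film at early termination if at least 6 weeks have passed since the previous one.

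**Conclusion.** The SAP contradicts itself on censoring for this supportive analysis, and the literal text of the 24-month definition and of Section 10.5.1.3 is unsuitable for an event seen only on film.

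A reader might infer three stronger things that the documents do not support:

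- **That the SAP has settled on the period-end rule.** Section 6.3 states the last-film rule and adopts it for the 24-month period, so the intended rule is open.
- **That the reported hazard ratio would be off by about 5%.** That is the second-year effect under the assumed 5% and 10%. The planned statistic is a single 24-month hazard ratio, which shifts by about 2%. The second-year figure would be reported only if proportional hazards failed and the piecewise model in Section 10.5.1.3 were used.
- **That the analysis makes the same assumption as the primary one, or was planned as a test of missing films.** The primary set generally leaves out women with no post-baseline film, so counting them as fracture-free is a different assumption. Section 10.5.2.2 claims only to show robustness.

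All shifts rest on assumed missing-film and early-termination-film rates. The hazard ratio moves visibly only if on-study women miss the Month 24 film at different rates by arm, and the direction follows the arm that misses more. The primary logistic test and its 95% power are untouched. This is a minor point, worth settling before unblinding.

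**What to change.** In Section 6.3, Time to First Event in 24-month Study Period, and in Section 10.5.1.3, add: for radiographic new vertebral fracture, subjects without an event are censored at their last post-baseline spine x-ray in the period, or at day 1 if there is none, as in the double-blind definition.

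Limit the sentence to that endpoint. Leave the censoring rules for clinical vertebral, nonvertebral and composite fracture endpoints unchanged; a broader phrase about vertebral fractures on x-ray could catch clinical vertebral fractures, which have their own Cox analyses. The primary analysis period definition needs no change, because no time-to-event analysis of new vertebral fracture is planned for that period.

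The cost is one sentence in two places and, if the code follows the period-end rule, one line of derivation. No data collection, sample size or primary analysis changes.

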### **Time to First Event in Month 12 to Month 24 Study Period**

Time to first event in Month 12 to Month 24 study period is defined similarly as for time to first event in 24-month study period. The reference date will be the start of open-label period.

### **Time to First Event in Primary Analysis Period**

The time to event in the primary analysis study period is defined similarly as for time to first event in double-blind period. Subjects who did not have any event will be censored on the date of last evaluation for the event, which is the end of primary analysis period date.

### **Time to First Event in Overall Study Period**

The time to event in the overall study period is defined similarly as for time to first event in double-blind period. Subjects who did not have any event will be censored on the date of last evaluation for the event, which is the End of Study Date recorded on the End of Study eCRF.

## **6.4 Fracture-related Study Endpoints**

All the fracture related efficacy endpoints are based on the results from the central imaging vendor analysis transferred to the Amgen database.

### **6.4.1 Trauma Severity Definitions**

#### **Low Trauma Severity**

Assessed by the investigator and collected on the Clinical Non-vertebral Fracture Summary eCRF for each clinical fracture event and includes

- Fall from standing height or less than 20 inches
- Minimal or moderate trauma other than a fall
- Unknown/don't know

#### **High Trauma Severity**

Assessed by the investigator and collected on the Clinical Non-vertebral Fracture Summary eCRF for each clinical fracture event indicating severe trauma other than a fall

#### **Pathologic Fracture**

Assessed by the investigator and collected on the Clinical Non-vertebral Fracture Summary eCRF for each clinical fracture event occurring from a pathology other than osteoporosis is deemed a pathologic fracture

### **6.4.2 Vertebral Fracture**

The types of vertebral fractures below are defined based on an assessment of spinal radiographs using Genant Semiquantitative Scoring Method ([Genant et al, 1993](#)), which is described in detail in [Section 13.2](#).

### **Imputation of Genant Grade for a Vertebra**

Because in an adult, a subject's vertebral fracture can only get worse or at best remain at the same severity over time, for the evaluation of prevalent vertebral fracture, any vertebra(e) with a missing grade at baseline will be assumed to have had a grade of 0 if the subsequent x-ray shows a grade of 0 for the same vertebra(e).

### **Prevalent Vertebral Fracture Status at Baseline**

Most subjects enrolled to this study will have at least one vertebral fracture. The most severe Genant semiquantitative grade from T4 to L4 at baseline is used to define the vertebral fracture status at baseline. A subject has a prevalent vertebral fracture if any vertebra from T4 to L4 has a grade of  $\geq 1$  at baseline. A subject does not have a prevalent vertebral fracture when all 13 grades from T4 to L4 are 0 on the first evaluable spinal radiograph collected during the study. Otherwise, the subject will have an unknown status for prevalent vertebral fracture.

### **Presence of Severe Vertebral Fracture at Baseline**

A subject has a prevalent vertebral fracture if any vertebra from T4 to L4 has a grade of 3 at baseline. Otherwise, a subject is considered absence of severe vertebral fracture at baseline.

### **New Vertebral Fracture**

A new vertebral fracture is identified when there is  $\geq 1$  grade increase from the previous grade of 0 in any vertebra from T4 to L4.

### **Worsening Vertebral Fracture**

A worsening vertebral fracture is identified when there is  $\geq 1$  grade increase from the previous grade of  $\geq 1$  in any vertebra from T4 to L4.

